1.0 Objectives

1.1 Describe the purpose, specific aims, or objectives of this research.

Response: To study the effects of transcranial direct current stimulation (tDCS) on weight and appetite.

Aim:

- 1. To compare weight loss over one month in active tDCS group with sham tDCS group. We will measure weight of every participants at the beginning of the study and one month after the last session of tDCS*
- 2. To compare change in insulin sensitivity over one month in active tDCS group with sham tDCS group. We will measure fasting insulin and glucose level, and calculate homeostatic model assessment-insulin resistance (HOMA-IR)*
- 3. To compare change in cognitive performance as a response to food over one month in active tDCS group with sham tDCS group. We will evaluate performance in a computerized task that measures executive functions under the presence of food (working memory, inhibitory control and a combination of both). We will assess changes in accuracy and speed in the task under active tDCS versus sham tDCS.*
- 4. To compare change in post-prandial glucose excursion and average meal counts per day. We will use continuous glucose monitor to record the frequency and amplitude of glucose excursion.*

1.2 State the hypotheses to be tested, if applicable.

NOTE: A hypothesis is a specific, testable prediction about what you expect to happen in your study that corresponds with your above listed objectives.

Response:

Hypothesis:

- 1. Active tDCS will result in more weight loss, appetite reduction and improved insulin sensitivity compared with sham tDCS over one month period.*
- 2. The effect of tDCS on weight, appetite, glucose tolerance and cognitive response to food varies according to the underlying allele status of BDNF and COMT gene*

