2.0 Scientific Endpoints

2.1 Describe the scientific endpoint(s), the main result or occurrence under study.

*NOTE: Scientific endpoints are outcomes defined before the study begins to determine whether the objectives of the study have been met and to draw conclusions from the data. Include primary and secondary endpoints. Some example endpoints are: reduction of symptoms, improvement in quality of life, or survival. Your response should **not** be a date.*

Response:

Primary endpoints: change in weight, measured as a percentage of baseline body weight.

Secondary endpoints: change in HOMA-IR, change in average daily meal counts based on frequency of glucose excursion on continuous glucose monitor, change in average amplitude of glucose excursion curve after meals, change in cognitive performance in response to food

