6.0 Inclusion and Exclusion Criteria

6.1 *Describe the criteria that define who will be **included** in your final study sample.*

NOTE: This may be done in bullet point fashion.

Response:

1. Men and women 18 to 80 years of age
2. Body mass index > 30 kg/m²

6.2 *Describe the criteria that define who will be **excluded** from your final study sample.*

NOTE: This may be done in bullet point fashion.

Response:

1. Current participation in any other concurrent clinical trials or previous participation within 30 days before the screening visit
2. Pregnancy or premenopausal women who are trying to be pregnant
3. Patients who are incompetent to give consent
4. Obesity due to a known secondary cause (Cushing's syndrome, hypothyroidism, etc) or a history of weight loss surgery

5. Have taken any of the following medications within the past 3 months:
phentermine, naltrexone, bupropion, topiramate, lorazepam, phendimetrazine, methamphetamine, benzphetamine, diethylpropion

6. Any contraindication to receive transcranial direct current stimulation (tDCS):

- Personal or family history of seizures, epilepsy or other unexplained loss of consciousness.
- Current or past history of skin disease or damaged skin on the scalp at the site of stimulation (i.e. eczema, skin with ingrown hairs, acne, razor nicks, wounds that have not healed, recent scar tissue, broken skin, etc.).
- Prior neurosurgical procedure or radiation.
- Known diagnosis of brain lesions, such as tumor, stroke or multiple sclerosis
- Implanted pacemaker, medication pump, vagal stimulator, deep brain stimulator, Transcutaneous Electrical Nerve Stimulation unit, ventriculo-peritoneal shunt or any metallic implant on the head.

6.3 *Indicate specifically whether you will include any of the following special populations in your study using the checkboxes below.*

NOTE: Members of special populations may not be targeted for enrollment in your study unless you indicate this in your inclusion criteria.

Response:

- Adults unable to consent
- Individuals who are not yet adults (infants, children, teenagers)
- Pregnant women
- Prisoners

6.4 *Indicate whether you will include non-English speaking individuals in your study. Provide justification if you will exclude non-English speaking individuals.*

In order to meet one of the primary ethical principles of equitable selection of subjects, non-English speaking individuals may not be routinely excluded from research as a matter of convenience.

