9.0 Recruitment Methods

N/A: This is a records review only, and subjects will not be recruited.

NOTE: If you select this option, please make sure that all records review procedures and inclusion/exclusion screening are adequately described in other sections.

9.1 *Describe when, where, and how potential subjects will be recruited.*

NOTE: Recruitment refers to how you are identifying potential participants and introducing them to the study. Include specific methods you will use (e.g. searching charts for specific ICD code numbers, Research Participant Groups, posted advertisements, etc.).

Response:

Participants will be identified by prescreening clinical charts prior to their clinic visit, and patient doctor interaction at the time of their visit at the Diabetes Endocrinology Center of WNY and Western New York VA Hospital. If the patient expresses interest after speaking with their physician and provide their contact information, they will be scheduled for a screening visit. The recruitment will start immediately after approval by IRB. Advertisements and flyers will be posted at these locations with the contact phone number for the patient to call the research team, if interested in participating.

Locations include:

1. [name]
2. [name]

3. [name]

4. [name]

9.2 *Describe how you will protect the privacy interests of prospective subjects during the recruitment process.*

NOTE: Privacy refers to an individual's right to control access to him or herself.

Response: HIPAA waiver is being requested, so that we will be able to use identifiable health information for subject recruitment. Any potential participant's personal health information will be kept solely between the study team and handled just as clinic patients' personal health information is handled. Locked file cabinets in locked offices for written data, password protected logins for electronic data, private rooms for any patient discussion. The data will only be shared with the study team who have all taken CITI training and will follow University privacy policies. We will not retain personal identifiers once the candidate is identified in the electronic medical record and contacted, no matter if the candidate agrees or declines to participate.

9.3 *Identify any materials that will be used to recruit subjects.*

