10.0 Procedures Involved

10.1 *Provide a description of all research procedures or activities being performed and when they are performed once a subject is screened and determined to be eligible. Provide as much detail as possible.*

NOTE: This should serve as a blueprint for your study and include enough detail so that another investigator could pick up your protocol and replicate the research. For studies that have multiple or complex visits or procedures, consider the addition of a schedule of events table in in your response.

Screening Day

All subjects will have completed the following procedures prior to participating in the study:

- 1) Informed consent
- 2) Medical history
- 3) Physical exam (including body mass index measurement)

We will collect general demographic data regarding years of education, race/ethnicity.

A continuous glucose monitor will be calibrated with finger blood glucose result and the probe of the monitor will be inserted into the abdominal subcutaneous tissue. Patient will be instructed on how to use continuous glucose monitor, they will be instructed to wear it and document the time and the types of food of every meal for at least 72 hours after the screening visit.

Subjects will be instructed not to change their medications during the whole study period and not to take insulin for at least 4 hours before visit 1, visit 5 and visit 6.

Visit 1:

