Continuous glucose monitor use is occasionally associated with insertion site discomfort or skin irritability. The effect is generally mild and resolve without intervention. We will demonstrate the correct way of using continuous glucose monitor to subjects to minimize the side effects. We will also ask them if they experience any side effects on the visit after continuous glucose monitor use and they are encouraged to report side effects over telephone.

The principal investigator [name], PhD and co-investigators [name] [name] and [name] will review the data of adverse reaction every 3 months to assess the safety and potential benefits to the participant. Furthermore, they will also assess other risks including the physical, psychological, social, legal and economic harm to these patients. The investigators listed above will carefully watch for any invasion of privacy and breach of confidentiality.

19.2 Describe what data are reviewed, including safety data, untoward events, and efficacy data.

Response:

Height, Weight, and adverse reaction reported by subjects are monitored every visit to ensure safety.

19.3 Describe any safety endpoints.

Response:

Adverse event (AE): Any untoward or unfavorable medical occurrence in a human subject, including any abnormal sign (for example, abnormal physical exam or laboratory finding), symptom, or disease, temporally associated with the subject's participation in the research, whether or not considered related to the subject's participation in the research

Serious adverse event (SAE): Any adverse event temporally associated with the subject's participation in research that meets any of the following criteria: 1) results in death;

2) is life-threatening (places the subject at immediate risk of death from the event as it occurred); 3) requires inpatient hospitalization or prolongation of existing hospitalization; 4) results in a persistent or significant disability/incapacity; 5) results in a congenital anomaly/birth defect; or any other adverse event that, based upon appropriate medical judgment, may jeopardize the subject's health and may require medical or surgical intervention to prevent one of the other outcomes listed in this definition (examples of such events include allergic bronchospasm requiring intensive treatment in the emergency room or at home, blood dyscrasias or convulsions that do not result in inpatient hospitalization, or the development of drug dependency or drug abuse)

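### Insulin users can enrol and are told not to change medication while less appetite and better insulin sensitivity are expected, yet nothing in the safety plan looks for unnoticed low glucose in the monitor traces

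*Combined protocol and SAP*

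**What the plan says.** **Who can enrol.** Section 6.1 admits adults aged 18 to 80 with a body mass index above 30. The drugs barred in section 6.2 are "phentermine, naltrexone, bupropion, topiramate, lorazepam, phendimetrazine, methamphetamine, benzphetamine, diethylpropion". None is a glucose-lowering drug, and diabetes is not an exclusion. A medication pump is a tDCS contraindication there, which may keep out insulin-pump users but not people who inject. Section 9.1 recruits by chart prescreening and "patient doctor interaction at the time of their visit at the Diabetes Endocrinology Center of WNY", as well as at a VA hospital.

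**What subjects are told.** Section 10.1 (Screening Day) states: "Subjects will be instructed not to change their medications during the whole study period". It continues with an instruction "not to take insulin for at least 4 hours before visit 1, visit 5 and visit 6". No exception for low glucose is given.

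**What is expected of treatment.** Hypothesis 1 in section 1.2 reads: "Active tDCS will result in more weight loss, appetite reduction and improved insulin sensitivity compared with sham tDCS over one month period".

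**What the monitor is for.** Section 2.1 lists two monitor endpoints: "change in average daily meal counts based on frequency of glucose excursion on continuous glucose monitor" and "change in average amplitude of glucose excursion curve after meals". Section 17.1 analyses those same quantities. Section 10.1 states downloads at Visit 1 and Visit 6 only.

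**What is reviewed for safety.** Section 19.2 answers: "Height, Weight, and adverse reaction reported by subjects are monitored every visit to ensure safety". No glucose value is named. The monitor risks in sections 19.1 and 21.1 are local to the insertion site, and low glucose is not among the risks in 21.1.

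**The concern.** Each statement is ordinary alone; the difficulty is the combination. A person on a fixed insulin regimen who eats less and becomes more insulin-sensitive is more exposed to low glucose, and those are the effects the trial hopes to produce. The medication rule, read as written, discourages the usual response.

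At stake is subject safety, not inference. A subject could have lows that he or she does not notice while the study holds a trace that shows them, with no one asked to look. Section 22.1 says subjects gain no direct benefit, so an avoidable risk that is cheap to reduce deserves attention.

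**Working it through.** The plan gives no figure to reproduce here. The check sets the sections side by side and counts days.

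**1. Are insulin users expected?** The 4-hour insulin hold in 10.1 makes sense only if some subjects take insulin. Section 6.2 does not exclude them, and the clinic named in 9.1 is a diabetes and endocrinology clinic. This is an inference, but a firm one. The number is not given: 0 to 20.

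**2. Does any stated route look for unnoticed lows?**

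| Route | Section | What starts it |
|---|---|---|
| tDCS safety questionnaire | 19.1, 21.2 | The subject reports something |
| Side-effect question after monitor wear | 19.1 | The subject reports something |
| Phone reporting | 19.4, 19.5 | The subject notices and calls |
| Investigator and staff availability | 12.1, 14.2, 14.3 | A request or known problem |
| Emergency deviation | 19.3 table | A recognised emergency |
| Withdrawal by the principal investigator | 20.1 | A known condition |
| Fasting glucose at Visits 1, 5 and 6 | 10.1 | Three single values, no safety limit stated |
| Halfway endpoint review | 19.7 | Study progress; not a check for lows |

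None assigns a person to search an individual trace for low values.

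**3. Timing.** Visits 1 to 5 fall on consecutive days and Visit 6 comes 4 weeks after Visit 5 (10.1).

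- Visit 1 to Visit 5: 4 days. Visit 5 to Visit 6: 28 days. Total: 4 + 28 = 32 days.
- Share of follow-up without a scheduled visit: 28/32 = 87.5%.
- Safety questionnaires: 5 sessions × 2 + 1 at the last visit = 11. Ten of them fall around the sessions, at Visits 1 to 5.
- Minimum planned wear after stimulation begins: 2 × 72 h = 144 h = 6 days, or 6/32 = 18.75% of follow-up (6/28 = 21.4% of the Visit 5 to Visit 6 interval).
- Days without required wear: 32 − 6 = 26, or 26/32 = 81.25%.
- Delay before the post-Visit 5 trace is downloaded, if worn for exactly 72 hours: 28 − 3 = 25 days.
- Cumulative safety review is every 3 months (19.7) and participation lasts about 2 months (11.2), so that review can come after a subject has finished.

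**4. Consequence for any trace check.** The Visit 1 download holds pre-stimulation data and Visit 6 is the last visit. A check tied only to those downloads would find no post-stimulation low before the subject's final visit.

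**The case against.** The strongest reply is that subjects are well looked after. An investigator is on hand throughout (12.1), the team provides coverage every day of the year (14.2), physicians can be reached (14.3), and the subjects are the team's own clinic patients (20.2). That stands. A reader might infer from the long gap after Visit 5 that phone reporting is then the only route; these sections show it is not. They are, however, reactive.

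A reader might also infer that doses are locked even in danger. The documents do not support that. The table in 19.3 provides for emergency deviations to protect a subject, 20.1 lets the principal investigator withdraw someone at risk, and the instruction in 10.1 is addressed to subjects and does not discuss physician-directed reductions. What remains is that no non-emergency exception for low glucose is written down.

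Nor do the documents support the inference that the traces go unread. Staff must process them for meal counts and excursion amplitude, and the adverse event definition in 19.3 covers abnormal findings, so a low that someone happened to see could be recorded. The gap is narrower: no limit, no named reader and no set time.

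Finally, the risk may be small. Section 17.2 calls the earlier effect on appetite and weight small, a monitor with a display or alarm would reveal some lows, and with no insulin users the main worry disappears. This bears on priority and is accepted in the verdict.

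**Conclusion.** The gap is real. Following the medication rule in 10.1 and the safety data list in 19.2 as written leaves unnoticed lows unexamined in traces the study already holds, and the reactive routes do not change that. The added risk cannot be quantified and is probably modest. A reader might infer that the trial exposes subjects to serious unmonitored harm; the documents do not show this.

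The conclusion assumes that at least one subject takes insulin or another glucose-lowering drug. It is also subject to three unknowns: the number of such subjects (0 to 20), whether the monitor displays readings or alarms, and whether the questionnaire or visit forms ask about low-glucose symptoms. No efficacy conclusion is affected. This is a cheap safety improvement that should be made, not an error that changes a result.

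**What to change.** For subjects on insulin or other glucose-lowering drugs:

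1. **Section 10.1.** State that a study or treating physician may reduce these drugs for safety, with drug, dose and date recorded. Keep the subject in the main analysis and cover the change in the section 17.1 sensitivity analysis.
2. **Section 19.2.** Have an existing investigator, blind to the stimulation code, read the screening trace at Visit 1 before the first session, and each later trace, against a low-glucose limit fixed before enrolment. If the limit is crossed, that investigator contacts the subject and records an adverse event.
3. **Timing.** Read the post-Visit 5 trace when that wear ends. Without this step the check detects nothing after stimulation until the last visit.
4. **Section 21.1.** List low glucose as a risk.

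**Cost.** Protocol wording, a short reading of data already collected, and one extra upload or monitor return per affected subject (0 to 20). Dose reductions may affect weight, the primary endpoint, or HOMA-IR, and 20 subjects cannot separate that from a treatment effect; the sensitivity analysis can only describe it. The check covers worn days only (at least 6 of about 32) and cannot prevent lows that have already occurred.

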
Breach of Confidentiality that caused harm or places subjects or others at increased risk of harm (physical, psychological, economic, or social harm (even if actual harm has not occurred).
	
Within 10 working days of knowledge or notification

Significant impact on the integrity of the research data
 
Examples:
 
 • Unplanned destruction of study records • Withdrawal of subject(s) impacts data integrity or causes inability to complete the study 	
Within 10 working days of knowledge or notification

Unanticipated Adverse Device Effects
 
Any serious adverse effect on health or safety of any life-threatening problem or death caused by, or associated with, an FDA regulated device, if that effect problem or death was not previously identified in nature, severity, or degree of incidence in the investigational plan or application, or any other unanticipated serious problem associated with a device that relates to the rights, safety, or welfare of subjects.
	
Within 10 working days of knowledge or notification

Any event/problem that would cause the sponsor to modify the investigator's brochure, informed consent document or would prompt other action by the IRB to assure protection of subjects.	Within 10 working days of knowledge or notification.
Any other “Serious” Event/Problem not described above	Within 10 working days of knowledge or notification

19.4 Describe how the safety information will be collected (e.g., with case report forms, at study visits, by telephone calls with participants).

Response:

On site during the visit. We also encourage participants to call us if they develop any adverse reaction

19.5 Describe the frequency of safety data collection.

Response:

The data collection will be done at all study visits. The patients, however, will be asked to report any adverse event or safety related information via phone as soon as it occurs.

19.6 Describe who will review the safety data.

Response: The safety data will be reviewed by the principle and sub investigators as well as the research coordinator.

19.7 Describe the frequency or periodicity of review of cumulative safety data.

Response: Safety data will be reviewed every three months during the duration of the study. Study endpoint data will be reviewed once after half of the recruited patients have completed the study and then at the end of the study.

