19.8 Describe the statistical tests for analyzing the safety data to determine whether harm is occurring.

Response: We will calculate the percentage of participants that developed any adverse reaction during the course of the study. We will use Fisher exact test to compare the percentage of participants that developed serious adverse reaction (which leads to withdrawal of subject) between group with active tDCS and sham tDCS. We will use two sample exact test for incidence rate data to compare the incidence of mild adverse reaction (which did not lead to withdrawal of subjects) between the two groups.

19.9 Describe any conditions that trigger an immediate suspension of the research.

Response: Inability to tolerate the tDCS administration, continuous glucose monitor or blood draw

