20.0 Withdrawal of Subjects

N/A: This study is not enrolling subjects. This section does not apply.

20.1 *Describe anticipated circumstances under which subjects may be withdrawn from the research without their consent.*

Response: Inability to tolerate the tDCS administration, continuous glucose monitor or blood draw. The principal investigator of the study can remove a participant from the research study without their approval if for any reason he/she feels is appropriate, including: severe side effect, injury or medical condition which may place subjects at risk of further complications if he/she continues to participate, failure to keep scheduled appointments, or other administrative reasons.

If any of the subjects become pregnant during the period of study, he/she will need to withdraw from the study.

20.2 *Describe any procedures for orderly termination.*

NOTE: Examples may include return of study drug, exit interview with clinician. Include whether additional follow up is recommended for safety reasons for physical or emotional health.

Response:

We will recommend that the subject come back for an exit visit to make sure he/she is not experiencing side effect from tDCS. However, they can also follow up with us in the clinic since the subjects are recruited from our clinic patients. They will also be asked to return the continuous glucose monitor after the study.

20.3 *Describe procedures that will be followed when subjects withdraw from the research, including retention of already collected data, and partial withdrawal from procedures with continued data collection, as applicable.*

Response: If a subject withdraws from the research, the data collected to that point will be used toward the research finding.

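### Section 19.8 sorts adverse reactions into serious and mild by withdrawal, which conflicts with the outcome-based SAE definition in 19.3 and mislabels the between-arm safety comparison

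*Combined protocol and SAP*

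**What the plan says.** Section 19.8 lists three safety outputs. The first is the percentage of participants with any adverse reaction, with no between-arm test stated. The second is a between-arm test: "We will use Fisher exact test to compare the percentage of participants that developed serious adverse reaction (which leads to withdrawal of subject"). The third is a "two sample exact test for incidence rate data to compare the incidence of mild adverse reaction (which did not lead to withdrawal of subjects").

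Section 19.3 defines an SAE by what happened to the subject: death, threat to life, persistent disability, congenital anomaly, an event that "requires inpatient hospitalization or prolongation of existing hospitalization", or one that may need intervention to prevent such an outcome. Withdrawal is not a criterion. The adverse event definition in the same section covers occurrences "whether or not considered related to the subject's participation in the research".

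Section 20.1 gives the grounds on which a subject may be withdrawn without consent. They include "Inability to tolerate the tDCS administration, continuous glucose monitor or blood draw" and, as reasons for which the principal investigator can remove a participant, "severe side effect, injury or medical condition which may place subjects at risk of further complications if he/she continues to participate".

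**The concern.** Two sections of one document use the word *serious* for different things. In 19.3 it describes the outcome of an event. In 19.8 it goes with whether the subject left the study. The sets overlap, but neither contains the other.

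Section 19.8 answers the template's question about how the data will show whether harm is occurring, and it holds the only between-arm tests of safety. If the *serious* row counts withdrawals, a zero there does not show that no SAE occurred, and a non-zero count does not show that one did. A published table with that label could mislead in either direction.

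**Working it through.** **1. The sorting rule.** The two parentheses in 19.8 mirror each other: *serious* goes with withdrawal, *mild* with no withdrawal. Together they assign every reaction by withdrawal status.

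**2. Does withdrawal follow every SAE?** Nothing in the documents says so. Section 20.1 says the principal investigator *can* remove a participant, and 19.1 says subjects with significant tDCS side effects *may* be excluded on the investigator's judgement. Both are discretionary.

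**3. The four combinations under the present wording.**

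| Meets 19.3 SAE criteria | Subject withdrawn because of it | Place in 19.8 |
|---|---|---|
| Yes | Yes | Serious, if regarded as a reaction |
| Yes | No | Mild if regarded as a reaction; otherwise in no between-arm test |
| No | Yes | Serious |
| No | No | Mild |

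The second and third rows are the conflict. A concrete case of the second follows from the visit schedule in 10.1: visit 5 is the last stimulation session and visit 6 comes four weeks later. A subject hospitalised in between has no stimulation left to stop and may simply attend visit 6. The third row could be filled by a withdrawal for intolerance under 20.1.

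**4. Event or reaction.** Section 19.3 speaks of events regardless of relatedness; 19.8 speaks of reactions, a term the protocol does not define. Sections 19.4 and 19.5 use both words for the same telephone reports: "We also encourage participants to call us if they develop any adverse reaction" and "will be asked to report any adverse event or safety related information via phone as soon as it occurs". Whichever word governs, an SAE without withdrawal stays outside the *serious* comparison.

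**5. How likely is a missing SAE?** There is no stated figure to reproduce, because the documents give no SAE rate. Let p be the assumed probability of an SAE per subject, w the assumed share of SAEs that lead to withdrawal, and n = 20 (section 5.1). The chance that at least one subject with an SAE is missing from the *serious* comparison is 1 − (1 − p(1 − w))^20. For p = 1% and w = 50%, this is 1 − 0.995^20 = 9.5%.

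| p (assumed) | w = 25% | w = 50% | w = 75% |
|---|---|---|---|
| 0.5% | 7% | 5% | 2% |
| 1% | 14% | 10% | 5% |
| 2% | 26% | 18% | 10% |
| 5% | 53% | 40% | 22% |

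**6. Effect on the Fisher test.** Section 10.1 gives a block size of 10 but no allocation ratio, so 10 v 10 is assumed. Two-sided p-values against zero are:

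| Split | p |
|---|---|
| 1 v 0 | 1.0 |
| 3 v 0 | 0.21 |
| 4 v 0 | 0.087 |
| 5 v 0 | 0.033 |

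One subject moved out of a 5 v 0 split takes the result from 0.033 to 0.087, but a split that large would be needed first. At two-sided 0.05, power is 0.1% for assumed rates of 10% v 2% and 12% for 30% v 2%. The damage is to the counts and their label far more than to any p-value.

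**The case against.** **The parenthesis may be a remark.** The first parenthesis can be read as saying that serious reactions are expected to lead to withdrawal, not as a case definition. Section 20.1 gives some support, since severe side effects, injuries and medical conditions are named grounds for removal. This reading cannot be excluded, but the matching *mild* parenthesis and the discretionary wording in 19.1 and 20.1 make withdrawal the working rule. Even as a remark, it does not agree with 19.3.

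**Safety oversight is intact.** A reader might infer that SAEs could escape notice. The documents do not support that. The reporting table in 19.3 follows outcome criteria, with deaths reported within 24 hours and the other listed outcomes within 72 hours. Section 19.7 has the safety data reviewed every three months. The suspension condition in 19.9 does not depend on the 19.8 tests. This objection stands, and it limits the point to the between-arm comparison.

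**Intolerance need not mean withdrawal.** A reader might infer that every intolerance will be counted as serious. Section 21.2 allows the glucose monitor alone to be discontinued, and 21.1 has the blood draw stopped for hypotension or dizziness. The over-count is possible, not certain.

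**SAEs may be rare and the test is weak.** Section 31.3 says that no major adverse effects were reported with these stimulation parameters, and the Fisher test has little power under either definition. Both are true. They bear on the size of the problem, not on whether the sections agree.

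**The rate test.** A reader might also infer that the incidence-rate test is invalid because 19.8 does not say how repeat reports are counted. That is an unstated detail, and the documents do not show an error in it.

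**Conclusion.** The conflict between 19.3 and 19.8 is real. Followed as written, 19.8 leaves an SAE without withdrawal out of the *serious* comparison, and it can put a withdrawal that meets no SAE criterion into it. This is a stated rule that yields a mislabelled result, not merely a missing detail.

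Its reach is small: the labels and counts of one between-arm safety comparison in a 20-subject pilot. The range of 2% to 53% for a missing SAE rests wholly on assumed rates. It shows that the case can arise; it does not estimate how often. The conclusion takes withdrawal as the sorting rule, which the mirrored wording favours but does not put beyond doubt. The wording should be changed because the present label can mislead and the repair costs almost nothing.

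**What to change.** Reconcile 19.8 with 19.3 as follows.

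1. Tabulate by arm, and compare with the Fisher exact test, the number of subjects with at least one SAE as defined in 19.3, whether or not they withdrew.
2. Keep the existing Fisher comparison of subjects withdrawn because of an adverse reaction, so that no planned between-arm test is lost. Label it *adverse reactions leading to withdrawal*, not *serious*.
3. Define the incidence-rate comparison as all reactions that do not meet the 19.3 SAE criteria, whether or not they led to withdrawal, and label it *non-serious*.
4. Use one term, *event* or *reaction*, throughout 19.3 to 19.8.

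A non-serious reaction that causes withdrawal will then appear under both 2 and 3, which the table should state.

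The cost is wording and one additional comparison on data already collected. With the power shown above, the SAE comparison will be mainly descriptive and should be presented that way. No clinical or withdrawal rule has to change.
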